10.3. Potential Benefits to Subjects

There are no benefits to participating in the study.

10.4. Alternatives to Participation

There is no alternative to participating in the study.

11. CONFIDENTIALITY OF DATA AND INFORMATION STORAGE

Confidentiality is the ethical and/or legal right that information, such as research data, will be held secret and safeguarded from disclosure unless consent is provided permitting disclosure. The subject data will be identified in the research data set using a unique random sequence of numbers. The random unique code along with all data sets related to the study will be maintained by the investigator and will be destroyed 36 months following the completion of data analysis.

The research data will be stored on a password protected file on an encrypted flash drive using a subject ID number. The flash drive will be stored in a cabinet in a locked office accessible only to the investigator. Transfer of research data will only occur on a computer between flash drives. Transfer of research data will not be done through email, cloud storage, or FTP or secure FTP.

12. RESEARCH INFORMATION IN MEDICAL RECORDS

Results of sialometry flow test will be recorded in the subject's dental chart.

13. DATA ANALYSIS AND MONITORING

13.1. Sample Size Determination

Because estimated durations of the test agents are not available, this pilot study is being undertaken. The number of subjects needed for this pilot study is 20, as recommended by the biostatistician.

13.2. Planned Statistical Analysis

After completion of the pilot study the number of subjects necessary for the definitive study will be calculated by the biostatistician.

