2. STUDY DESIGN

2.1. Overview

This double blind controlled randomized crossover study is designed to determine the duration of effect of a single dose of Biotène Moisturizing Mouth Spray. Because no detailed information about the duration of its effect is available now, a pilot study to determine sample size will be completed first. The spray consists of a mixture of starch, polymers, and plant oils which act as humectants to moisturize the oral tissues as well as flavorings that serve as salivary stimulants (Jose et al. 2016). Subjects complaining of a dry mouth will be recruited from the Division of General Dentistry of the Eastman Institute for Oral Health. Potential subjects will be scheduled for a screening appointment during which they will sign an informed consent form, complete a questionnaire about their experience with xerostomia, and then undergo a measurement of unstimulated whole saliva flow rate (UWSFR). Those whose UWSFR is \leq 0.2mL/min. will be admitted to the study and will then be administered a dose of either the experimental or control (water) agents. The unstimulated whole salivary flow rate of 0.2 mL/min is selected because it is widely recognized as the level at which actual mouth dryness occurs (Coulter et al, 2008). Statistical analysis will focus primarily on comparing the duration of action of the two agents but also collecting qualitative information about subjects' experiences with xerostomia and the two agents.

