3. CHARACTERISTICS OF THE RESEARCH POPULATION

3.1. Subject Characteristics

Pilot Study

In order to establish adequate power at an acceptable level of significance for this study, an estimate of the duration of effect of the experimental and control is needed. At this time no such information is available; therefore a pilot study will be completed, as suggested by the study statistician ([name], PhD). Results of the pilot will help determine the minimum number of subjects required for a definitive study. The following describes the characteristics of the population for the pilot study:

- a) **Number of subjects:** A total of 20 subjects enrolled is suggested by the biostatistician. A subject is considered in the total count once informed consent has been obtained and the inclusion criteria met. To account for dropout and disqualification of eligible subjects, 50 subjects will be recruited.
- b) **Gender and age of subjects:** Adults aged 18 years and over will be enrolled with no regard to gender, although it is recognized that xerostomia in the general population is more prevalent in older adults and in females (Fox et al. 1985).
- c) **Racial and ethnic origin:** Subjects will be recruited without regard to race or ethnicity.
- d) **Vulnerable subjects:** Vulnerable subjects (as defined by University of Rochester IRB Criteria) will not be enrolled.

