5.2. Efficacy Assessment

This pilot study was developed because estimated data regarding the duration of action of a single dose of Biotène Moisturizing Mouth Spray is not available. The estimated duration is necessary for calculating the sample size for a definitive study. At the completion of the pilot, the mean duration of action of both the experimental and control agents will be forwarded to the biostatistician ([name]) for calculation of the sample size for the definitive study. When the required sample size is returned to investigators, plans for the definitive efficacy assessment will be developed.

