8.1. Biotène Dry Mouth Moisturizing Spray

Biotène Dry Mouth Moisturizing Spray (Appendix 12) contains water, polyglycol, propylene glycol, sunflower oil, xylitol, milk protein extract, potassium sorbate, acesulfame

K, potassium thiocyanate, lysozyme, lactoferrin, lactoperoxidase (45 mL). No maximum dosage or interval for usage is specified. Product is to be used *ad libitum*. The Investigational Drug Lab at the University of Rochester Strong Hospital, [name] will be supplying, packaging, and labeling the product as well as the placebo which will consist of distilled water.

The agent of interest is IND/IDE exempt for this clinical investigation as the product is lawfully marketed in the United States for the treatment of symptoms of dry mouth [FDA 21 CFR 312.2(b)/FDA 21 CFR 812.2(c)].

8.2.Dosage of Study Drug/Biologic

For the purpose of this study, 3 streams of the product (approximately 0.5 mL) administered by the investigator will be considered a dose. For consistent dosing, two sprays to prime the spray nozzle will be completed prior to administering a dose to the subject.

8.3.Subject Enrollment/Randomization

Subjects will be allocated to group A or group B using block randomization (Appendix 6). Subjects will be allocated to a group as they qualify for the study. The subject and the investigator will be blinded to the group a subject is allocated to. The products will be labeled identically except for a serial code on the bottle will correspond to the treatment or control. The true identity of the products will be known only to the supplier (the Investigational Drug Lab, University of Rochester Strong Memorial Hospital), and unknown to the investigator and subjects until the completion of the study.

8.4.Accountability of Investigational Supplies

The Investigational Drug Lab of the University of Rochester Strong Memorial Hospital, [name] will be responsible for the formulation and labeling of investigational supplies. The Investigational Drug Lab will be the unblinded third party. The investigator will handle the receipt, storage, dispensing, collection, accountability log, and disposal of the investigational supplies.

8.5.Subject Withdrawal of Study Drug

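### No analysis is stated for the crossover comparison; the only summary named, one mean duration per agent, ignores pairing and randomised sequence and cannot size the definitive study

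*Combined protocol and SAP*

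**What the plan says.** Section 2.1 sets the design and the aim: "This double blind controlled randomized crossover study is designed to determine the duration of effect", and "Statistical analysis will focus primarily on comparing the duration of action of the two agents". Section 8.3 allocates the sequence: "Subjects will be allocated to group A or group B using block randomization". Appendix 4 prints the randomisation table in blocks of six.

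Section 13.2, headed as the planned statistical analysis, consists of one sentence: "After completion of the pilot study the number of subjects necessary for the definitive study will be calculated by the biostatistician". It names no test, no paired analysis, no period term and no sequence term, and no other section supplies one.

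The only outcome summary named is in Section 5.2, where "the mean duration of action of both the experimental and control agents will be forwarded to the biostatistician" so that the definitive sample size can be calculated. Plans for the definitive efficacy assessment are put off until that number is known. Section 13.1 gives the pilot size: "The number of subjects needed for this pilot study is 20, as recommended by the biostatistician".

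**The concern.** In a two-sequence crossover the information lies in each subject's own difference between agents. The randomised sequence is what allows a visit effect to be separated from the agent effect. Here the sequence is randomised and then never used.

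Two things are at stake. First, the pilot exists to size a later study. A crossover is sized from the SD of the within-subject differences, and two means do not contain it. Second, if a paired SD is later taken without regard to sequence, any visit effect inflates it and carries into the definitive N.

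A visit effect is plausible from the documents. The flow limit of 0.2 mL/min must be met at Visit 1, whereas at Visit 2 subjects continue whatever their flow (Section 5.1.1), so regression to the mean is possible. The endpoint is the subject's own decision to stop a timer, and Visit 1 is the first time the subject does this in the study. The washout of at least 48 hours deals with carryover and the fixed morning window with time of day. Neither removes a visit effect.

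**Working it through.** **The plan's own figure.** The pilot N of 20 cannot be reproduced. It is a recommendation, with no alpha, power, effect or SD given.

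**Inputs from the documents.** Two periods, two sequences, N = 20 (13.1), blocks of six (Appendix 4), duration capped at 120 minutes (5.1.1 and Appendix 10).

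**Inputs assumed.** SD of the paired difference within a sequence, s = 30 minutes; visit effect p = 10, 15 or 20 minutes; 1:1 allocation with three of the six block numbers mapped to each group; two-sided alpha 0.05; 80% power.

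**Model.** Let τ be the Biotène minus water difference, p the Visit 2 minus Visit 1 effect, n1 the number given Biotène first, n2 the number given water first, and N = n1 + n2. The paired difference has mean τ − p when Biotène comes first and τ + p when water comes first.

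- Unadjusted mean difference: τ + p(n2 − n1)/N.
- Unadjusted variance of the differences: s² + p² × 4·n1·n2/[N(N − 1)], which is about s² + p².
- Period-adjusted estimate: the average of the two sequence means. It is unbiased for τ, with SE = (s/2)√(1/n1 + 1/n2) and N − 2 degrees of freedom.

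**Inflation of required N**, 1 + p²/s²:
- p = 10: 1 + 100/900 = 1.11
- p = 15: 1 + 225/900 = 1.25
- p = 20: 1 + 400/900 = 1.44

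For a 10-minute difference, N = (1.96 + 0.84)² × (s² + p²)/10². This gives 71 with the within-sequence SD, against 79, 89 and 103 with the unadjusted SD.

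**Precision in the pilot at 10:10.** The adjusted SE is (30/2)√(1/10 + 1/10) = 6.71 minutes. For p = 15 the unadjusted variance is 900 + 225 × 400/380 = 1136.8, so the SE is √(1136.8/20) = 7.54. For p = 10 and 20 it is 7.09 and 8.13. In simulation (40,000 runs), power for a 20-minute difference at p = 15 was 73% unadjusted and 80% adjusted. With no true difference, the unadjusted test rejected in 2.9% of runs, so at 10:10 the fault is lost power and not false positives.

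**Bias.** Its size is p × |n2 − n1|/N: zero at 10:10 and 2p/20 = 0.10p at 11:9, which is 1.0, 1.5 and 2.0 minutes for the three values of p.

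**Chance of 11:9.** Three full blocks give 9:9. The last two subjects come from a block with three places per group, so they fall in the same group with probability 2 × (3/6) × (2/5) = 0.40. The printed table is fixed. Reading its first 20 entries along rows or down columns, with 1–3 against 4–6 or odd against even, gives 10:10 in two of the four readings and an 11–9 split in the other two.

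**Cost of adjusting when p = 0.** Calculated power for a 20-minute difference goes from 80.7% to 80.5% at 10:10, and from 80.7% to 80.1% at 11:9.

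**The case against.** The strongest reply is that the plan has not chosen a poor analysis. A reader might infer that the comparison is planned as two unpaired means with sequence ignored. The documents do not support that: Section 13.2 plans no comparison at all, and the means in Section 5.2 are inputs to sizing. Silence is not a decision to ignore sequence, and a biostatistician given the raw data could do the right analysis. This stands as far as it goes, but the text as written passes on figures that cannot do the job it assigns them.

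A reader might also infer that a period effect is likely. That goes too far. Both sessions share the same morning window and the same recording procedure, and no figure for a visit effect is given. The xerostomia questionnaire is no firm evidence of a difference between visits either: Section 5.1.1 places it at Visit 1, while Appendix 6 lists a survey of xerostomia experience under Session 2.

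A reader might further infer serious bias from unequal groups. With complete data and equal sequences, the difference of the two agent means equals the period-adjusted estimate. A bias of 0.22p would need 11:7 (4/18 = 0.22), that is, two losses both from the smaller group and neither replaced. Section 7 provides for replacement when numbers fall short, and Section 3.1 plans a margin: "To account for dropout and disqualification of eligible subjects, 50 subjects will be recruited". The replacement rule does not, however, protect sequence balance.

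Finally, the 120-minute cap means the additive model is only approximate if many durations reach it. That is correct, and the fix asks for the count.

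**Conclusion.** The point holds as a gap with a ready remedy. The crossover analysis is unspecified, and the one named summary lacks the pairing, the sequence and the SD needed to size the next study. That much rests on the text alone.

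The size of the harm is conditional. At an assumed SD of 30 minutes, leaving a visit effect of 10 to 20 minutes in the paired SD raises the definitive N by 11% to 44%. If there is no visit effect, nothing is lost on this count, but two means still cannot size a crossover. The bias is minor: zero at 10:10 and 0.10p at 11:9, a split with probability 0.40 under the assumed mapping of block numbers, which the documents do not state. All values in minutes are assumptions for illustration.

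**What to change.** In Section 13.2, state that the pilot comparison of agents is the within-subject difference in duration adjusted for period. Either compare period differences between the two randomised sequences (Hills-Armitage), or fit a mixed model with agent and period fixed and subject random. Either is adequate; name one in advance. Report the difference in minutes with a 95% CI and the number of subjects in each sequence.

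In Section 5.2, replace the forwarded per-agent means with the period-adjusted mean difference and the within-sequence SD of the paired differences. Report alongside them how many durations reach the 120-minute cap, so that the biostatistician can judge whether a linear summary is adequate.

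The cost is protocol wording and one degree of freedom (19 to 18 with 20 complete subjects). No new data, visits or subjects are needed.

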13.3. Data and Safety Monitoring

Data and safety monitoring by the principal investigator is appropriate because the study is considered minimal risk and will be conducted at a single site. Prompt reporting of reportable events and other study-related safety information will be made to the RSRB and sponsor.

Appendix 1 – Example script for screening subjects at the recruitment encounter

Investigator:

Hello, I understand you have heard of our study and may be interested in participating. Are you age 18 or older?

Potential subject:

Yes No

Investigator: (If “yes”):

Do you frequently have the feeling of dryness of your mouth that gives you discomfort at times of the day in addition to when you first wake from sleep?

Potential subject:

Yes No

Investigator: (If “yes”):

Do you regularly (at least daily) use any type of medication or product other than water to help relieve the feeling of dryness?

Potential subject:

Yes No

Investigator: (If “no”):

Proceed to next question

Investigator: (If “yes”)

Would you be willing and able to cease using the product for at least 48 hours (2 days) before each of the two test visits required by the study?

Investigator: (If “No”)

I’m sorry then you would not be a candidate for this study. Thank you anyway.

Investigator: (If “Yes”)

[figure not shown]
If Yes

Fine, then let’s look for an appointment for your first test visit. Please know, however, that at this first visit, we must perform a test of your saliva for which you will be given \$25 plus the cost of your parking. If the results show a certain result, we will want you to return for a second and final visit. If not, we must dismiss you from the study at that time.

If, however, we find that we do have the result required by the study, we will then schedule an appointment for the final visit, for which you will receive a payment of \$50 plus the cost of your parking.

Do you have any questions?

Thank you for your interest in our study.

[figure not shown]
Appendix 2 – Flow diagram for screening subjects at the recruitment encounter

Appendix 4 – Six Block Randomization Table

At enrollment, subjects will be randomly allocated to a number from 1-6 using the random blocks shown above. The true identity of the products (Biotène or distilled water) will be known only to Investigational Drug Services, University of Rochester Strong Memorial Hospital.

523164	123465	521364	241563	435162	214653
254163	345612	251634	246153	164325	436512
561234	134562	615342	432561	546132	642413

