As subjects qualify for the study, they will be placed, according to a randomization table (Appendix 4), in either one group (Group A) or the other (Group B). If a patient being recruited is found not to meet the inclusion criteria, s/he will be dismissed and the next potential candidate will be evaluated for admission to the study.

Patients will be assured that their regular clinical care will not be affected by their decision to participate or not participate in the study. Similarly, enrolled subjects who withdraw from the study will be assured that they will continue to receive their regular clinical care.

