5. The same cup will be handed to the subject and will be used for collection of the sample of whole saliva over a period of 15 minutes.

The organization and administration of the test agents will be completed in the laboratory of [name], Pharm D, Manager of Investigational Drug Services (IDS) here at the University. Each bottle of test agent (either Biotène Dry Mouth Moisturizing Spray or sterile water) will be appear in identical spray bottles. The possibility exists that the investigator or subject may notice the scent and viscosity differences between the different agents, however this will unlikely impact the outcome measures. To assess the impact of these differences, the post-test questionnaire (Appendix 11) will ask subjects if they think they received the moisturizing spray or the alternative (sterile water). The spray bottles will be unlabelled except for a unique number which identifies the contents to IDS laboratory and the statistician. The true identities of the bottles will be unknown to the investigator and the subjects. The contents of the test agent will be linked to each subject through a randomization process completed by IDS.

A recent study (Jose et al, 2016) sponsored by the manufacturer (GlaxoSmithKine) of Biotène spray investigated the comparative effect of 3 of its products with 2 hours as the primary endpoint. Since xerostomia lasting longer than 2 hours may be uncomfortable, demonstrating that an agent provides relief close to this time frame would have potential therapeutic and commercial value. Although the study design was different, 49.5% of subjects reported that the spray was good, very good, or excellent at “relieving the discomfort of dry mouth” 2 hours after use of the spray. A previous study (Shahdad et al. 2005) also discovered that most subjects achieved relief utilizing topical agents after 2 hours. In this study involving a Biotène gel, it was found that the viscosity is positively correlated to the retention time of the agent (Shahdad et al. 2005). Therefore, we expect the less viscous experimental spray to have a shorter retention time than the expected 2 hours. Therefore, 2 hours will be defined as the maximal endpoint in this study. We expect that the crossover design and qualitative measures will aid health care providers and patients to derive benefit from Biotène Moisturizing Mouth Spray or water.

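### The protocol prints the upcoming code sequence, with the same six codes in every block, so a code recognised once can reveal the agent order for later subjects; the sections on codes and randomisation also disagree

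*Combined protocol and SAP*

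**What the plan says.** Four places describe the allocation.

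- **Section 4.1:** as subjects qualify, "they will be placed, according to a randomization table (Appendix 4), in either one group (Group A) or the other (Group B").
- **Appendix 4** ("Appendix 4 – Six Block Randomization Table"): 18 blocks of six digits are printed, and "subjects will be randomly allocated to a number from 1-6 using the random blocks shown above". Product identity is "known only to Investigational Drug Services, University of Rochester Strong Memorial Hospital".
- **Section 8.3:** "Subjects will be allocated to group A or group B using block randomization (Appendix 6"). Appendix 6 is the checklist of study procedures. The same section says that "a serial code on the bottle will correspond to the treatment or control".
- **Sections 5.1.2 and 5.1.3:** each bottle carries a unique number, and "The contents of the test agent will be linked to each subject through a randomization process completed by IDS". This text also accepts that the investigator or the subject may notice differences in scent and viscosity.

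One investigator role covers the steps that matter. The investigator sees potential subjects for screening (section 4.1), gives the sprays (section 2.3), receives, stores and dispenses the supplies (section 8.4), and repeats the discomfort question every 15 minutes (section 5.1.1). The endpoint is the moment at which the subject feels that the effect has gone. On size, section 13.1 says: "The number of subjects needed for this pilot study is 20".

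**The concern.** A code list protects the trial only while the codes tell the enrolling and dosing person nothing. Here the sequence is in the protocol, the block length is fixed and visible, and only six codes are in use. If a code always stands for the same group, recognising the agent in one subject informs on more than that subject. It gives the order of agents for every later subject with the same code, and the printed table shows when that code comes up next.

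At stake is advance knowledge of agent order by the person who decides whom to enrol and when, who sprays, and who prompts for ratings of a purely subjective endpoint. The documents also leave it unclear which system operates: six recurring codes taken from a table, or unique bottle numbers under a list run by IDS.

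**Working it through.** The plan gives no figure of its own on this point, so there is none to reproduce.

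**Inputs.** 18 printed blocks of six (Appendix 4); 20 subjects (section 13.1); 50 to be recruited (section 3.1). Two assumptions are not in the documents: each code keeps one meaning throughout, and, where stated, three codes belong to each group.

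**1. Carry-over after one block.** A valid block contains each of codes 1 to 6 once. If the agents are recognised in the first six subjects, all six codes are known. Later subjects: 20 − 6 = 14, and 14/20 = 70%.

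**2. Faster or slower recognition.** With three codes per group there are C(6,3) = 20 possible maps from code to group. Reading the table by rows:

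- After three recognised subjects (codes 5, 2, 3), those codes recur 7 times among subjects 4 to 20: three in block two, three in block three, one in the first two places of block four. In 2 of the 20 maps these three codes make up one whole group, so all 17 later subjects are known. In the other 18 maps, 7 are known. Average: (2×17 + 18×7)/20 = 160/20 = 8 of 17.
- After five recognised subjects the sixth code follows by elimination, so all 15 later subjects are known.

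**3. The last printed block.** Seventeen of the 18 blocks contain each of 1 to 6 once. The last, 642413, has 4 twice and no 5. It fills positions 17×6 + 1 = 103 to 108. Twenty subjects need 4 blocks (20/6 rounded up) and 50 need 9, so in printed order it is not reached. The first three blocks give 9:9 and the last two subjects bring the split to between 9:11 and 11:9, with or without the faulty block.

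**4. The texts side by side.** Appendix 4 and section 4.1 have subjects allocated from a printed table of six recurring numbers. Sections 5.1.2 and 5.1.3 have IDS do the randomisation and give bottles unique numbers. The documents do not say how a subject's number from 1 to 6 relates to the bottle number. Unique bottle numbers alone would not stop the carry-over if the investigator also sees the subject's number and that number keeps one meaning. If the investigator never sees it and cannot infer it from the table, the carry-over does not arise.

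**5. Choice of block size.** If past assignments and the block size are known, a block with m subjects per group forces on average a share 1/(m + 1) of its assignments: 1/2 for blocks of 2, 1/3 for blocks of 4, 1/4 for blocks of 6. Smaller blocks are therefore more predictable, not less.

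**The case against.** Four points can be made for the plan.

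- **The key is not printed.** Appendix 4 and section 8.3 keep product identity with the drug service (section 5.1.2 adds the statistician). Reading the next digit reveals nothing until codes are linked to agents. This stands. A reader might infer from the printed table that allocation is open to the investigator; the documents do not support that. That the investigator has the protocol to hand is itself inferred from the role.
- **Recognition unmasks a dosing whatever the label says.** If scent or viscosity gives the agent away, a unique code does not restore masking for that subject. This also stands. What recurring codes add is mainly knowledge of the order before enrolment and dosing. In a crossover every subject receives both agents, so selecting subjects by order is a limited threat that works mainly through period effects. The subject, not the investigator, stops the timer.
- **The plan foresees the risk.** Appendix 11 asks subjects which product they think they received, partly to judge whether better masking is needed later. This stands in part: the investigator's guess is not collected.
- **Section 5.1.2 already describes unique numbers and randomisation by IDS.** This is close to the remedy, but it does not settle the matter, because Appendix 4 and section 4.1 describe something else.

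A reader might also infer that the faulty last block unbalances the trial. It lies beyond 20 and beyond 50 subjects in printed order. It may also be an error in reading the PDF: one changed digit would make it valid, and the text refers to blocks above it although they now follow it. Any probability that the block is used would need a rule for drawing blocks at random, which the documents do not contain.

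**Conclusion.** The concern holds in a conditional form. The code sequence is exposed in fixed blocks of six with recurring codes, and the plan itself accepts that the agents may be recognised. If each code keeps one meaning and the investigator recognises the agents, the order is known in advance for up to 14 of 20 subjects after one block. With three codes per group, the figures are on average 8 of 17 after three recognised subjects and 15 of 15 after five. If codes are not recognised, or if IDS in fact issues unique numbers under a list that the investigator cannot trace, the exposure is much smaller or absent. The documents contradict themselves on which of these applies, and that alone needs correction. They do not show that allocation is openly revealed, that masking has failed, or that balance is lost in this pilot.

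**What to change.** 1. Reconcile section 4.1, sections 5.1.2 and 5.1.3, section 8.3 and Appendix 4 into one description of who allocates, from which list, and what the subject number and the bottle number each mean. Correct the reference to Appendix 6 in section 8.3.
2. Take the sequence out of the protocol. Have IDS generate, check and hold the list.
3. Use a unique, non-repeating bottle code for each subject and visit, for subjects not yet randomised and in the definitive study. This is the essential part.
4. Do not disclose the block size. Fixed blocks of 4 would give 10:10 at 20 randomised subjects (20 = 5 × 4). Avoid blocks of 2.
5. Appendix 13 is a call script for people already enrolled, so enrolment appears to have begun. Document which list was used for them and whether codes repeated.
6. Minor: check block 642413 against the source document and correct it if the error is real.

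The cost is generating one list and relabelling bottles. If the pilot is under way this is a mid-trial change and should be recorded as such.
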